Current recommendations from the American College of Chest Physicians (ACCP) evidence-based guidelines for the management of pulmonary lesions begin with the determination of whether the lesion is stable or has benign calcification.^{1,4} If the lesion is stable or benign, no further evaluation is warranted; otherwise, management decisions are based on surgical risk and on the clinical probability that the lesion is malignant. For patients with <5% probability, repeat imaging is recommended at variable time intervals up to 2 years, and for patients with high probability of cancer (>65%), tissue diagnosis with VATS followed by resection is recommended. Those patients with lesions of intermediate probability for malignancy require more complicated evaluation.

The various recommended procedures for obtaining tissue diagnosis in these intermediate cases include transthoracic needle aspiration (TTNA), surgery, and flexible bronchoscopy (FB). The diagnostic yield with FB varies with lesion size and location. Based on review of 10 studies using FB for diagnosing peripheral pulmonary nodules (PPN), the sensitivity is only 34% for lesions <2cm and has been found to be as low as 14%.^{5,6} The sensitivity increases to 63% when lesions are >2cm in size, but decreases as the distance from the hilum increases. A lesion having a bronchus sign (the finding of a CT-visible bronchus leading to the lesion) increases the success of transbronchial biopsy and brushing.⁷ The ACCP recommends that nodules without a CT-bronchus sign should be pursued with TTNA unless radial endobronchial ultrasound (R-EBUS) is available.⁶ Bronchoscopy is commonly used for pulmonary masses, but the yield, while high, does not approach 100%.

Several new technologies have evolved which allow clinicians to reach pulmonary lesions with bronchoscopy: electromagnetic navigation (ENB), ultrathin bronchoscope, R-EBUS, virtual bronchoscopy (VB), endobronchial ultrasound (EBUS), and guide sheath.

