Despite new technologies that have arisen in the last decade for bronchoscopic biopsy of peripheral pulmonary lesions, the sensitivity for FOB remains as low as 34% for lesions < 2cm and increases to around 63% for lesions >2cm in size, but decreases again as the distance from the hilum increases. The use of R-EBUS as an adjunct is recommended as it increases diagnostic yield. A biopsy approach using R-EBUS through an ultrathin scope, guide sheath and fluoroscopy may increase the diagnostic yield of pulmonary lesions even further when compared to standard FB with fluoroscopy; it may also improve the utility of bronchoscopy for the diagnosis of peripheral pulmonary lesions thereby decreasing the need and risk associated with TTNA. This study will also evaluate the radiographic and procedural factors that have been described to influence that diagnostic yield.

II. RESEARCH DESIGN AND METHODS

This is a multi-center, prospective, randomized controlled trial to evaluate the diagnostic yield of two standard of care bronchoscopy procedures used to biopsy peripheral pulmonary lesions identified on chest CT: (1) standard FB using an adult standard bronchoscope (Olympus BF-180) with fluoroscopy, and (2) bronchoscopy using the BFP-190 ultrathin bronchoscope in combination with R-EBUS and guide sheath.

Primary outcomes: Diagnostic yield of standard FB with fluoroscopy using standard adult bronchoscope versus bronchoscopy using ultrathin bronchoscope in combination with R-EBUS with or without guide sheath for lung lesions 1.5-5 cm.

Secondary Outcomes:

- 1) The radiographic and procedural factors that influence the diagnostic yield including the size and location of the lesion, the distance from the main carina, the number and type of specimens obtained, and the location of sampling within the lesion.
- 2) Adverse event rates of hemoptysis and pneumothorax.

DEFINITIONS:

Lung lesions: solid nodules or masses 1.5-5 cm in diameter

SUBJECT ENROLLMENT (See Figure 1):

Subjects presenting to their standard of care pulmonologist in need of a bronchoscopic biopsy of their peripheral pulmonary lesion as part of their standard medical care, and who meet study inclusion/exclusion criteria, will be invited to participate. A total of 214

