patients will be enrolled. As this is a competitive enrollment study, MUSC will enroll up to 75 volunteers. Eligibility will be determined by each site PI. The PI or Co-I will explain the study to qualified subjects prior to obtaining consent. The subject will also be given an opportunity to review and sign documentation of HIPAA compliance and authorization.

Inclusion criteria:

Patients to be included for participation in this study are:

- 1) Patients with a solid lung lesion 1.5-5cm identified on chest CT (obtained within previous 3 months) with the intention to undergo bronchoscopic evaluation. If the lesion is partially solid (i.e. there is a ground glass component) then the solid portion must make up >75% of the lesion and measure at 1.5-5cm. The decision to pursue biopsy will be made by the treating physician and agreed upon by the patient. This will include patients determined to have an intermediate risk of malignancy (5-65%) and those non-surgical candidate with higher risk lesions in need of diagnosis for alternative treatment. OR
- 2) Patients with a solid lung lesion 1.5-5cm identified on chest CT (obtained within previous 3 months) that are surgical candidates with a high probability of cancer (>65%) will be referred for surgical evaluation. If the lesion is partially solid (i.e. there is a ground glass component) then the solid portion must make up >75% of the lesion and measure at 1.5-5cm. If the patient refuses surgery or if the surgeon requests a definitive diagnosis prior to surgery the patient will have the option to be included in this study. All sites will use the same online calculator to document probability of malignancy.
- 3) Patients whose targeted lung lesion is visualized with fluoroscopy
- 4) Are at least 22 years old,
- 5) Lack Bleeding disorders, and
- 6) Are able to provide informed consent.

Race and gender inclusion will reflect the population characteristics found in the respective regions.

Exclusion criteria:

Patients to be excluded from participation in this study are:

- 1) Patients with a pure ground-glass opacity identified on chest CT
- 2) Patients with endobronchial involvement seen on chest CT.
- 3) Patients who refuse to participate,
- 4) Are less than 22 years of age,
- 5) Lack fitness to undergo flexible bronchoscopy as determined by the bronchoscopist prior to procedure, and
- 6) Are unable to provide informed consent
- 7) Pregnant

INFORMED CONSENT:

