Each site investigator will review the results, and the results will become part of the subject's medical record and research record. Any clinical follow-up or repeat procedures will be dictated by the patient's physician based on clinically relevant data and will not be influenced by enrollment into this study. To protect subject

confidentiality, MUSC will receive all sites' data as de-identified through use of the 6 digit patient codes. All information and data related to this study will be stored in a secured, locked cabinet in MUSC Clinical Sciences Building Room 809. The privacy of subjects will be protected using a 6 digit computer generated random code. The key to the code will be kept in a password protected folder on the MUSC DB2 (\DA) server; access to this folder is restricted to study personnel alone.

Electronic Data will be entered and stored in the secure REDCap database created for this study. REDCap is a web-based application designed exclusively to support data capture for research studies. It provides an intuitive interface for data entry, audit trails for tracking data manipulation and export procedures, procedures for importing data from external sources, advanced features such as branching logic and calculated fields, and automated export procedures for seamless data downloads to common statistical packages such as SPSS, SAS, Stata, and R. It was developed at Vanderbilt University (see <http://redcap.vanderbilt.edu/consortium/index.php>) and is ideal for remote data entry, as will be the case for this multi-center trial.

III. STATISTICAL ANALYSIS:

Statistical comparisons will be made using chi-square analysis where applicable. Sensitivity, specificity, positive and negative predictive value and accuracy of all procedures will be calculated. A logistic regression analysis of factors influencing tissue quantity will be undertaken.

Coordinating Center: MUSC will be the designated coordinating center for this trial. MUSC will be responsible for development of the database, housing the data, working with the sites on IRB issues, patient enrollment, completion of on-line data collection instrument and validation of the data. MUSC will also be responsible for payment to the sites when a patient's case report form is complete and query-free. Statistical support and interim analysis will be performed at MUSC by an in house statistician ([name]). Interim results will be shared with all participating sites during teleconference meetings.

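### Optional improvement, not an error: a pre-specified test of yield stratified by lesion size would add about 3 points of power in a reference case built on the cited 34%/63%, and from near zero to about 7 under other assumed inputs

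*Combined protocol and SAP*

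**What the plan says.** Section III names one method for comparing groups: "Statistical comparisons will be made using chi-square analysis where applicable". It does not mention stratification, covariates or continuity correction. The only regression is for a different outcome: "A logistic regression analysis of factors influencing tissue quantity will be undertaken". Yet secondary outcome 1 concerns "factors that influence the diagnostic yield including the size and location of the lesion".

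On size as a predictor, the Background states for standard bronchoscopy that "the sensitivity is only 34% for lesions <2cm and has been found to be as low as 14" per cent, and then: "The sensitivity increases to 63% when lesions are >2cm in size".

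Size must be known from chest CT for eligibility (1.5-5 cm), and Data Collection item (1) records the longest-axis diameter. Subject Randomization describes a 1:1 schedule overall and states no stratification by size. Bronchoscopy Procedures sets 107 patients per arm for 85% power, assuming yields of 50% and 70% and a two-sided alpha of 0.05.

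**The concern.** When a baseline variable predicts a binary outcome, a crude comparison carries the between-stratum variation as noise. Here the protocol cites a 29-point difference in sensitivity across 2 cm and already collects size, but names no analysis of the primary outcome that uses it. What is at stake is some power and a slightly narrower confidence interval. Naming the adjustment in advance also avoids choosing one after the data are seen. Chance imbalance in size between the arms is not bias, and the argument does not rest on it.

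**Working it through.** **1. The plan's own figure.** Inputs from Bronchoscopy Procedures: n = 107 per arm, yields 0.50 and 0.70, two-sided alpha 0.05. With the pooled-variance formula:

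z = [0.20 × √107 − 1.96 × √(2 × 0.60 × 0.40)] / √(0.25 + 0.21) = 1.048, so power = 85.3%.

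Exact enumeration of the uncorrected chi-square gives 85.0%. The stated 85% reproduces. With a continuity correction the crude chi-square has about 81.7%.

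**2. Gain from size adjustment, by formula.** Let w be the share of lesions under 2 cm, and gC and gT the yield gaps (larger minus smaller lesions) in the standard and R-EBUS arms. Overall yields are held at 50% and 70%.

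- Crude: V0 = 0.25 + 0.21 = 0.460. On this unpooled scale, power is 86.2%.
- Size-standardised: V1 = V0 − w(1 − w)(gC + gT)²/2.
- Power = Φ(0.20/√(V/107) − 1.96).
- 95% CI half-width = 1.96 × √(V/107).

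Reference case: use 34% and 63% as yields. The mix that averages to 50% is w = (0.63 − 0.50)/0.29 = 0.448. Take +20 points in both strata, so gC = gT = 0.29.

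- V1 = 0.460 − 0.448 × 0.552 × 0.58²/2 = 0.418, and V1/V0 = 0.910.
- Power rises from 86.2% to 89.2%, a gain of 3.0 points.
- The half-width falls from 12.9 to 12.3 points.
- The gain is worth 214/0.910 = 235 patients, or 21 more than planned.

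**3. Range, with simulation.** 107 per arm, unstratified randomisation, 400,000 trials per case (1,000,000 for no size effect). Power in %; the formula gain is in points.

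| Assumed inputs | V1/V0 | Formula gain | Chi-square, uncorrected | CMH, uncorrected | CMH, corrected |
|---|---|---|---|---|---|
| Reference: w = 0.448, gaps 29/29 | 0.910 | 3.0 | 84.9 | 88.2 | 85.0 |
| w = 0.30, gaps 29/29 | 0.923 | 2.6 | 85.0 | 87.9 | 84.6 |
| w = 0.143 (sizes even over 1.5-5 cm: 0.5/3.5), gaps 29/29 | 0.955 | 1.5 | 85.0 | 86.8 | 83.4 |
| w = 0.448, gaps 20/20 | 0.957 | 1.4 | 85.0 | 86.6 | 83.3 |
| w = 0.448, gaps 15/15 | 0.976 | 0.8 | 84.9 | 85.9 | 82.4 |
| w = 0.448, gaps 29/0 | 0.977 | 0.8 | 84.9 | 85.7 | 82.3 |
| w = 0.143, gaps 15/15 | 0.988 | 0.4 | 85.0 | 85.6 | 82.1 |
| w = 0.143, gaps 15/0 | 0.997 | 0.1 | 85.0 | 84.9 | 81.4 |
| Cited 14% v 63%: w = 0.13/0.49 = 0.265, gaps 49/49 | 0.797 | 6.5 | 85.1 | 92.1 | 89.5 |
| Same, gaps 49/0 | 0.949 | 1.7 | 85.0 | 86.5 | 83.1 |
| No size effect, w = 0.448 | 1 | 0 | 85.1 | 85.1 | 81.6 |

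In the 14%/63% case with equal gaps, the half-width is 11.5 points.

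**4. Type I error.** Under the null, the uncorrected chi-square rejects in 4.7-4.8% of trials and the uncorrected CMH in 4.9-5.0%. A small part of the simulated gain is therefore test size.

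**The case against.** The strongest reply is that no defect exists. The chi-square is valid and meets its power target. CMH is itself a chi-square statistic, so the wording does not rule it out. That stands, and it is why this is only a suggestion.

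The second reply is that 3 points is not what 34% and 63% give by themselves. The 45% mix is back-solved, and it puts nearly half the lesions in the lowest 0.5 cm of a 3.5 cm range. The equal gap in the R-EBUS arm is also assumed. With R-EBUS yield flat across size the gain is 0.8 points. If all the benefit is in lesions under 2 cm it is 0.1. The cited figures are sensitivities, not yields. They may overstate this trial's gap, because lesions under 1.5 cm are excluded and the lesion must be seen: "Patients whose targeted lung lesion is visualized with fluoroscopy". All of this stands, so the result should be read as a range. Nor is 7 points a ceiling: a 49-point gap with near-equal strata, or all the benefit in lesions over 2 cm, reaches about 8.6 to 9.

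Third, adjustment could cost power. With a reversed size gradient under R-EBUS (85%/58% against 34%/63% for standard), simulated power is 84.9% for chi-square and 84.8% for CMH, which is negligible.

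Fourth, the type I error check covers a single look. Section III also plans an interim analysis, which these simulations do not cover.

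**Conclusion.** The point holds as an optional improvement. The planned test is sound, and its 85% power is correct for the uncorrected version. Pre-specified stratification by size adds about 3 points of power in the reference case, with a gain between near zero and about 7 points across the other cases tested. No case tested shows a meaningful loss, and single-look type I error stays at about 5%. Confidence in the size of the gain is moderate, because the size mix, the size gap within 1.5-5 cm and R-EBUS yield by size are all assumed. The gain also depends on the test version: a continuity-corrected CMH has 85.0% power in the reference case and 81.4-84.6% in the less favourable ones, which cancels the benefit over the uncorrected chi-square.

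**What to change.** In section III, name the single primary test of diagnostic yield: a CMH test without continuity correction, stratified by lesion size (<2 cm v ≥2 cm). Report the size-standardised risk difference with its 95% CI, and state the variance formula. Keep the crude chi-square, also without continuity correction, as a sensitivity analysis.

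In Data Collection item (1) and the case report form, add a measurement rule: longest-axis diameter of the lesion, read from the pre-randomisation eligibility CT and recorded before the envelope is opened, for every patient including those with part-solid lesions. Two places make the rule necessary. Bronchoscopy Procedures lists CT images among the steps that follow randomisation. For part-solid lesions the eligibility size is that of the solid part ("then the solid portion must make up >75% of the lesion and measure at 1.5-5cm"), whereas Data Collection measures the lesion.

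The cost is one sentence in the statistical section, one measurement rule and a case report form entry that all sites complete before randomisation. It needs no new imaging and no change to the sample size.

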Multicenter, prospective, randomized trial of bronchoscopy with ultrathin bronchoscope and radial endobronchial ultrasound (R-EBUS) with fluoroscopy versus standard fiberoptic bronchoscopy (FB) with fluoroscopy for biopsy of pulmonary lesions

Principal Investigator: [name], MSCR

Co-Investigator: [name], MS

Contact information:

[name], MS

Professor of Medicine

Medical University of South Carolina

[contact]

[contact]

Email: [contact]

OBJECTIVES

The goal of this study is to evaluate radial endobronchial ultrasound (R-EBUS) for the diagnosis of pulmonary lesions ($\geq 1.5\text{cm}$). Accessing pulmonary lesions is problematic because they are often not visible endobronchially, may not be large enough to be easily visualized by fluoroscopy for transbronchial biopsy (TBBx), and/or are surrounded by damaged lung making the transthoracic approach difficult. In this study, we hope to evaluate new technologies to aid in transbronchial biopsy using R-EBUS to facilitate location and sampling of tissue.

SPECIFIC AIMS:

1. To compare the diagnostic yield of R-EBUS with the BFP190 ultrathin bronchoscope and fluoroscopy versus standard fiberoptic bronchoscopy (FB) with fluoroscopy in the evaluation of lung lesions 1.5-5cm.
2. To assess factors that may influence yield:
 - a. radiographic characteristics – size, location, distance from visible bronchus, PET characteristics
 - b. procedural characteristics – number of passes, type of specimen obtained [brush, forceps biopsy, site of biopsy (within vs. adjacent to lesion), rapid on-site evaluation (ROSE) diagnosis

I. BACKGROUND

Pulmonary lesions are a common but difficult issue for primary care and specialty physicians and are often found incidentally on Chest X-Ray (CXR) or Computed Tomography (CT) scan.¹ With the results of the National Lung Cancer Screening Trial demonstrating a reduction in lung cancer mortality with screening of high risk patients with low dose CT scan, the number of nodules detected requiring follow up is likely to increase exponentially as 25% of those screened had a detected lung abnormality.² In studies of incidentally detected nodules, the prevalence of malignancy ranges from 2-82%,³ the problem for clinicians is deciding on the management and further diagnostic modalities to pursue.

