The risks associated with bronchoscopy are collapsed lung, breathing difficulty, vocal cord spasm, vomiting, dizziness, bronchial spasm, infection, low blood oxygen, heart attack and bleeding from biopsied site. The occurrence of these risks is extremely low. The measures to mitigate the risks are the same as for all bronchoscopy. To minimize the chance of bleeding, all patients will be questioned about tendency to bleed prior to bronchoscopy as per standard care. Anticoagulation with antiplatelet agents will be held according to guideline recommendations for that drug.²⁵ If bleeding occurs, patients will be treated with direct pressure, local instillation of epinephrine or electrocautery. Vocal cord spasm will be prevented through the use of lidocaine on the vocal cords. Patients with lung disease may receive bronchodilators prior to bronchoscopy at the discretion of the performing bronchoscopist. There is no way to reduce the minimal risk of infection due to bronchoscopy since the scope must go through the naso or oropharynx. Patients are given supplemental oxygen and their oxygen level is continuously monitored using pulse oximetry. Patients ECG, heart rate, blood pressure, and blood oxygen are continuously monitored by a nurse, respiratory therapist and physician during the

procedure. If there is any sign of a worsening in status, such as elevated heart rate, low oxygen, or ECG changes, the procedure will be aborted.

RESEARCH ONLY RISKS

Risk of breach in confidentiality

Every effort will be made to protect the privacy of the research subjects. All information and data related to this study will be maintained in secured, protected space, and access will be restricted to study personnel only.

DATA COLLECTION:

Prior to each site initiation, the site PI and staff will participate in an educational teleconference with the Coordinating Site PI to ensure that all personnel fully understand the protocol, data collection instrument, and any other study related issues or documents. Contact information, including the phone and pager numbers for the principal investigators and study staff will be provided to all sites

Data on the following will be collected at all sites: radiographic characteristics, procedural characteristics, diagnostic yield, crossover to other procedures, confirmation of diagnosis, and complications:

(1) Radiographic Information:

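### The plan's only regression models tissue quantity, while Aim 2 and secondary outcome 1 ask which factors influence diagnostic yield

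*Combined protocol and SAP*

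**What the plan says.** Section III (Statistical Analysis) contains three analytic statements:

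- a general one on tests: "Statistical comparisons will be made using chi-square analysis where applicable";
- a list of accuracy measures (sensitivity, specificity, predictive values, accuracy) to be calculated for all procedures;
- one regression: "A logistic regression analysis of factors influencing tissue quantity will be undertaken".

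The question about factors is put in three other places, each time with yield as the outcome:

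- Specific Aims, Aim 2: "To assess factors that may influence yield". Item 2b includes among those factors "number of passes, type of specimen obtained".
- Rationale: "This study will also evaluate the radiographic and procedural factors that have been described to influence that diagnostic yield".
- Section II, Secondary Outcomes, item 1: "The radiographic and procedural factors that influence the diagnostic yield including the size and location of the lesion". Its list of factors ends with "the number and type of specimens obtained, and the location of sampling within the lesion".

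The Data Collection section says that sites will collect "radiographic characteristics, procedural characteristics, diagnostic yield, crossover to other procedures, confirmation of diagnosis, and complications".

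**The concern.** The outcome of the only specified model is not the outcome of the aim. Run literally, the regression would use a variable that is undefined and that no aim asks about. Aim 2 and secondary outcome 1 would then rest on chi-square tests for which neither outcome nor factor is stated. The model, the coding of continuous factors and the form of the outcome would be settled at analysis. Aim 2 is one of only two specific aims, so a reader of the results would want to know that its analysis was fixed beforehand.

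**Working it through.** This is a mismatch between passages, so the check is mainly a comparison of text.

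**1. Which outcome is modelled?** Aim 2, the Rationale and secondary outcome 1 name yield or diagnostic yield. Section III names tissue quantity. No regression of yield appears anywhere in the document.

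**2. Could the model be run as written?** A logistic model needs a categorical outcome. Tissue quantity occurs once in the document, with no unit, threshold or categories. Data Collection, item 2 (Procedural Characteristics), lists number of passes, types of biopsy, R-EBUS description of the biopsy site, duration and sedation. None of these is a measure of tissue quantity, and the other Data Collection items contain none either.

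**3. Could the term stand for something that is recorded?** The closest items are number of passes (Aim 2b) and number of specimens (secondary outcome 1). Both are listed as factors that may influence yield. Reading tissue quantity as one of them would put a candidate predictor in the place of the outcome.

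**4. Do the other sentences fill the gap?** The accuracy measures describe procedures and do not examine factors. Chi-square could test a categorical factor, such as lobe or specimen type, against yield one factor at a time. It could not use lesion size, SUV or generations from the main carina without cut-points, and none is given. It also gives no adjusted estimates. Adjustment matters here because the Background and Rationale say that sensitivity rises with lesion size and falls with distance from the hilum. The two effects therefore need to be considered together.

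**5. Is yield a workable dependent variable?** Yes. Data Collection, item 3, already separates a biopsy giving a specific diagnosis, whether cancer or benign disease, from a non-diagnostic one, with chronic inflammation grouped with the latter. That is a per-patient yes/no outcome.

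**6. Are the primary comparison and sample size touched?** The inputs are in Bronchoscopy Procedures: yields of 50% and 70%, two-sided alpha 0.05, power 85%. With pooled variance under the null and no continuity correction:

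n per arm = [1.960 × √(2 × 0.6 × 0.4) + 1.036 × √(0.5 × 0.5 + 0.7 × 0.3)]² / 0.20² = (1.358 + 0.703)² / 0.04 = 106.2, rounded up to 107.

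Power at 107 per arm is 85.3%. The stated figure reproduces, and nothing in it depends on tissue quantity.

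**The case against.** The strongest reply is that this is a drafting slip. A logistic model suits yield and does not suit an undefined quantity, and the sentence echoes the wording of Aim 2. The aim is exploratory and unpowered, so a statistician would probably model yield anyway. That is plausible and limits the likely harm. It does not remove the point, because Section III is the governing text and it names another outcome.

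A second reply is that Aim 2 asks only to assess factors, and chi-square can do that. This stands in part: Aim 2 is not without any method. What remains is set out in step 4 of the working.

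A reader might also infer more than the documents support:

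- *That the factors themselves are left open.* They are named in Aim 2 and secondary outcome 1. The outcome, the model and the coding are what is missing.
- *That a specimen count would hardly vary.* One brushing and five biopsies, six samples, are set for each assigned procedure completed as planned. But a standard-arm patient whose ROSE is non-diagnostic or shows chronic inflammation goes on to the R-EBUS protocol. That can add another six, making 12 in all. The procedure may also be aborted or changed if the lesion cannot be located.
- *That a yield model would be overloaded with terms.* The plan gives no coding for location or any other factor, so such a figure would describe an assumed model and not this plan.

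**Conclusion.** The point holds as a mismatch between the specified regression and the stated secondary aim. The text is wrong as written, and more than a detail is missing. No corrected number follows from it. Its size is one secondary aim, corresponding to secondary outcome 1, with no regression specified for its outcome. It gives no ground for doubting the primary arm comparison or the 107 per arm.

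The conclusion rests on reading Section III as the operative analysis text and on tissue quantity having no definition elsewhere in the document. Confidence in the mismatch is high. Whether the sponsor would actually have analysed tissue quantity is uncertain. The correction is worth making before analysis.

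**What to change.** In Section III, replace the regression sentence so that it states:

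- **Dependent variable:** diagnostic yield of the assigned procedure, scored as a specific diagnosis (cancer or benign disease) against a non-diagnostic result, with chronic inflammation counted as non-diagnostic, in line with Data Collection, item 3.
- **Explanatory variables:** study arm and the factors already named in Aim 2 and secondary outcome 1.
- **Restricted factors:** SUV only in patients who had PET, biopsy site only where R-EBUS was used for the procedure being scored, and ROSE only where it was performed (it is specified for all patients in the standard arm).
- **Tissue quantity:** delete it, or define it as a separate outcome with its own categories and data item.

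The cost is a few sentences and a little analysis work. Design, sample size and procedures do not change. Data collection would change only if tissue quantity were kept as an outcome.
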